Aim 6: From the QUIC scale two scores are calculated: 1) the Informed Consent Aggregate Score (ICAS) and 2) the Therapeutic Misconception Aggregate Score (TMAS). ICAS assesses the quality of consent, ranging from 0-10 (10 is a perfect score) and TMAS assesses the presence of a therapeutic misconception (TMAS), ranging from 0-5 (5 is a perfect score). The ICAS and TMAS scores will be calculated and the means and standard deviations summarized for all participants. We will also summarize individual questions to understand the quality of specific elements of informed consent process. We will compare ICAS and TMAS between women in different stages of labor using one-way ANOVA, and with different pain scores using Spearman correlation and linear regression. Multiple

linear regression will be used to assess the independent association of covariates of interest (demographics, stage of labor, pain score, anxiety, obstetric history and trust) with ICAS and TMAS scores.

Aim 7: Using the motion metric on the wireless device we will summarize mobility in the first 24 hours after their cesarean both as a continuous variable ,and categorizing women into those with low and high mobility. We will summarize the functional status of women in the post discharge period according to the five dimensions measured by the mobility survey : (ability to move independently, ability to selfcare, ability to perform usual activities, level of energy, and overall health, as well as a composite variable with scores of 1-4. 1 being poorest functional status and 4 being better functional status) We will describe functionality at the different time points after discharge using frequency and percent. We will compare return to functionality at the different time points by mobility category in the first 24 hours using regression modelling. We will also describe the rates of impoverishing and catastrophic expenditure after surgery. Summary statistics will be calculated for all expense types. We will compare impoverishing and catastrophic expenditure rates between women with different functional status and early mobility.

Sample Size:

On average approximately 8-10 emergency cesarean deliveries are performed at MRRH daily. Thus, in a two week block we estimate ~ 112 emergency cesareans performed. We plan to capture all women delivered by emergency cesarean during an intervention block thus minimizing the risk of selection bias based on the severity level. Assuming 85% of women consent to participation (conservative estimate based on >90% recruitment in prior studies)^{5,74,75}, this yields an estimated 95 women per block. Over 12 months of enrollment, we will therefore have 13 intervention blocks and 13 control blocks. This yields an estimated 1,235 women in the intervention group and 1,235 in the control group. Assuming an intraclass correlation coefficient of 0.01, the effective sample size after taking account of clustering is 633 per group. This will allow us to detect a difference of 5.7% in the SMO rate between the two study arms, with a two-sided significance level of 0.05, and 80% power, assuming a baseline rate of SMO of 13% ^{71,73}

Risk/Discomforts and protections

Clinicians:

- Risk of false alerts, alert fatigue: Clinicians will be asked to hold a mobile phone and respond to alerts. It is possible that alerts of physiologic sign abnormalities may not correspond to a developing or established clinical abnormality and in responding to the alert clinicians may become fatigued from alerts. Study investigators will monitor for this occurrence and the impact on clinician performance and duties and adjust study protocols as necessary
- Risk of diversion and interruptions to work on other patients: Alerts sent to clinicians may also prompt them to perform additional exams or clinical procedures that may or may not be beneficial to the patients from which alerts were received. This may divert attention or human resource away from other clinical needs. We will monitor for any diversions resulting in substandard clinical care. If these occur we will consider protocol modifications. Any safety concerns or adverse events arising because of false alerts or diversions will be communicated to the IRB within 10 days.

Peripartum women:

- Theoretical risk of exposure to radio emissions from Wi-Fi from the biosensor: There is a theoretical risk of exposure to Wi-Fi signals from the biosensor worn by women participating in

the study. The FDA has indicated the majority of studies dealing with radio emissions from devices, such as mobile phones, have failed to show an association between exposure to radiofrequency from a cell phone and health problem. Regulatory bodies in both the United States and Canada have set Specific Absorption Rates (SAR) of <1.6 watts per kilogram, for radio emitting devices such as Bluetooth devices and cell phones sold in the United States. The SAR indicates the rate at which energy is absorbed when exposed to radio frequency. Mobile phones in the United States transmit in the range of 0.25 watts per kilogram when used near the ear. Bluetooth devices transmit a SAR of 0.001 watts per kilogram. Based on this data, Radiofrequency emissions from the biosensor are significantly lower than cell phone transmissions (Federal Communications Commission, "OET Bulletin 56: Questions and Answers about Biological Effects and Potential Hazards of Radiofrequency Electromagnetic Fields," www.fcc.gov, Aug. 1999). Moreover the biosensor and monitoring system to be used in this research protocol has been tested MRRH and approved for general use by the FDA

- Mild discomfort/skin irritation from wearing the device: The biosensor to be used is attached to the sternum using standard adhesives for electrode applications which have been approved and are in routine clinical use. In preliminary work women reported high acceptability related to the comfort of the device^{18,31}; however, this study will require women to wear a different device and for a longer period of time and during a phase where breastfeeding is likely to occur. To minimize this risk, potential participants with known allergies or hypersensitivity to device materials will be excluded from the study. In addition, we will actively monitor for safety concerns (e.g. skin irritation, physical discomfort, disruptions to breastfeeding, and emotional concern with the monitoring) throughout the above described procedures through observation of the participants. We will review all reports of safety concerns within 24 hours and communicate any adverse events to the IRB within 10 days. The study team will also facilitate referral for any necessary medical care. If any adverse events are deemed related to the biosensor device, the study will be stopped until the safety issue is resolved.
- Risk of additional clinical interventions or exams that may or may not be beneficial: Alerts of abnormal physiologic signs may prompt doctors to perform additional exams and clinical interventions. If abnormalities in physiologic signs do not correspond to developing or established clinical abnormalities this may mean additional procedures are performed without benefit. We will monitor for any substandard clinical care to participants, or participant distress caused by this and modify study protocols as necessary.
- Less than 24 hours between recruitment and consent: As noted above peripartum woman will be approached for recruitment into the study once admitted to the unit for delivery to allow monitoring to begin immediately after delivery. Due to this timeline, there will be less than 24 hours between initial approach and consent. Particularly given the high intensity time around childbirth, this exposes the women to some vulnerability in decision-making. The RA recruiting and seeking consent will be carefully trained to fully explain the risks and benefits and to ensure women understand that they will still receive current standard of care at the hospital should they decline to participate. Women indicating interest in participating will be approached again once the decision has been made for an emergency cesarean delivery. Due to potential unpredictable changes in clinical course and the development of complications that may render a woman unable to provide consent for herself, we have limited enrollment to those women who can either consent for themselves or who have a guardian available to consent for themselves. Consent via a guardian is included as monitoring critically ill women who may be unable to provide their own consent is paramount to ultimately affecting clinical outcomes

Both clinicians and peripartum women:

- Stress and anxiety related to study procedures: Post-graduate doctors may experience some stress and anxiety due to the requirement to hold the responder phone particularly given they

will have other clinical responsibilities at the same time e.g. performing other procedures and evaluating other patients. Study investigators will actively monitor for impact on clinicians. We will review all reports of safety concerns within 24 hours and communicate any adverse events to the IRB within 10 days. 2) Any woman undergoing childbirth can have high levels of physical and emotional stress. Research participation during process may increase this stress and anxiety. During recruitment of both doctors and women it will be emphasized that participation is voluntary, and they are free to decline to participate or drop out at any point without repercussion.

- Risk of fatigue from interviewing: In depth interviews will be designed to take less than one hour. However, this time frame may induce fatigue in participants. We will ensure interviews last no more than one hour, and the qualitative RA is trained to take regular breaks as needed. Participants will be informed in advance that they can take a break or stop at any time. As there are two types of qualitative interviews, we will ensure that no one participant has to participate in more than one interview.
- Loss of privacy and confidentiality: Participants in all studies are subject to loss of privacy and confidentiality. In particular, physiologic sign data from postpartum women will be transferred to a central CPU or tablet for display and review by clinicians and abnormalities in physiologic signs sent a responder phone. In addition, medical information extracted from charts could be subject to loss of privacy. To ensure confidentiality all data will be maintained on password-protected, encrypted computers (if electronic) and/or locked cabinet (if hardcopy). All interviews will be held in a private location at a time convenient to the interviewee. All data, other than physiologic sign data for clinician review, will be coded by subject number. All RAs and interviewers will receive training on procedures for maintaining privacy.

Potential Benefits

Doctors will benefit from having easier and more timely access to physiologic data, reducing their work burden and improving their ability to more fully care for their patients. Postpartum women will have the direct benefit of increased physiologic monitoring. In some cases, this can be life-saving as developing complications may be averted from earlier intervention. In addition, I anticipate that wireless maternal monitoring will ultimately help reduce rates of maternal and newborn morbidity and mortality, particularly in resource-limited settings. The results of the proposed study will help establish the preliminary efficacy of this strategy for monitoring and how to improve implementation. Furthermore, understanding mobility in the postpartum period and the financial risks associated with childbirth and its recovery, may help us reduce these risks and improve recovery from cesarean deliveries. Both type of participants may feel good about contributing to research in this area.

Monitoring and Quality Assurance

Prior to conducting the study, the research assistants will receive training on how to use the data collection tool, as well as standard clinical research ethics (i.e., the online CITI course available through Massachusetts General Hospital [MGH]).

A member of the study staff will verify completion of data as entered into the chart review forms prior to data analysis. Missing or inconsistent data that can be verified with the participant's chart or interviewed clinician prior to discharge will be entered retrospectively. Data that cannot be verified with the participant or their chart will not be included in data analysis. All quality control measures will be performed on a weekly basis and as needed.

Qualitative data will be transcribed within 48 hours of data collection and then translated into English if need be.

The principal investigators shall provide oversight and review of study protocols throughout the study. Quality checks will be performed on a weekly basis by the principal and co-investigators to ensure accurate data collection.

The principal investigators will review all potential instances of privacy violations or other concerns within 24 hours and communicate any adverse events to the MUST and MGH IRBs within 10 days.

A Data and Safety Monitoring Board (DSMB) will be convened.

Our chosen DSMB will include the following

1. [name] – Former Chair Dept of OB/GYN Makerere University
2. [name] – Lecturer, Dept of Medicine, MUST
3. [name] – Associate Professor of Global Health and Social Medicine, Biostatisticia, Harvard Medical School

The DSMB will meet 4 times during the anticipated 12-month study duration (prior to initiation, twice during the study, and at the end). Stopping rules will be discussed by the DSMB at the first meeting to establish criteria against which study progress and safety are measured at each further DSMB meeting. Specifically, we will ask the DSMB to review if there is a signal of higher rates of severe maternal outcome than expected to determine if these are related to the study intervention and then provide recommendations to study changes including but not limited to potential consideration of study termination. We will also ask their assistance in monitoring study implementation, including participant burden.

Additionally, we will convene a community advisory board who will review the planned study prior to its beginning and provide a resource for advice and recommendation should unexpected challenges arise during study implementation. We will again meet with the community advisory board to help disseminate the findings of our research to the community.

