The wireless monitor to be used is a wearable wireless vital sign monitor called Current™. The device provides continuous real-time transmission of oxygen saturation, respiration rate, pulse rate, temperature, motion and activity, and posture captured every 2 seconds. It is integrated with the Omron Evolv blood™ pressure cuff to allow automated capture of blood pressure. Physiologic data from the sensor is transmitted via WiFi to a secure cloud storage (hosted by Amazon Web Services). Current™ is fully HIPAA¹ compliant and HITRUST² certified and has received US FDA approval. Physiologic data can then be accessed via a secure password protected mobile phone app or displayed on a monitor for real-time viewing. Pre-defined criteria can be used to program alerts or notifications should vital signs fall outside of the range. These notifications can be received via SMS or a mobile app notification. Notifications can be sent to multiple providers at a time. Providers can also log on or off from the device corresponding to their duty shifts.

To complete Aim 1, we will enroll all willing attending doctors and staff midwives with clinical duties covering the maternity ward, emergency cesarean delivery and postoperative care during the study period to use the wireless physiologic system and receive message alerts. Due to staffing the numbers of clinicians may fluctuate during the enrollment period. We will also enroll 1235 women undergoing emergency cesarean delivery during the study period during intervention blocks to wear a wireless physiologic monitor for 24 hours after birth. An additional 1235 women, also undergoing emergency cesarean during the study period during non-intervention blocks, will form a control group and have medical record review only. *We request to waive consent for this record review only.* Clinicians and peripartum women participating in wireless physiologic monitoring will form the same participants for Aim 2, which will involve participant observation, record review, and retrieval of data from the wireless monitoring system and clinician responder phones. To complete Aim 3, We will perform semi-structured interviews on 30 clinicians and 30 postpartum women drawn from

¹ HIPAA: Health Insurance Portability and Accountability Act of 1996) is United States legislation that provides data privacy and security provisions for safeguarding medical information

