1. Inability to speak English or Runyankole	Lack of available interpreters for effective communication in other languages; It is anticipated 100% of clinicians at this facility speaks one of these two languages

Peripartum Women

Inclusion criteria	Rationale
1. Age >18	We will exclude women under the age of 18 because even if they are considered emancipated minors, most are not adults physiologically. Our research questions are designed to study physiologic monitoring in adult women, and may not apply equally to pregnant children under the age of 18. Moreover, this the wireless device currently only has food and drug safety approval for adult use.
2. Undergoing emergency cesarean delivery at MRRH	Women undergoing emergency cesarean are chosen due to increased risk of morbidity and mortality in this population. Additionally, the study proposes to test monitoring in the first 24 hours after birth, therefore women delivered outside of MRRH and arriving in the postpartum period will arrive after this period has begun and will miss the critical window to initiate monitoring.

3. Able to provide consent or have a guardian/attendant present who can consent on their behalf.	The latter is included as monitoring critically ill women who may be unable to provide their own consent is paramount to ultimately affecting clinical outcomes
4. Willing to wear the biosensor for 24 hours	
5. Willing to remain in the postpartum unit for 24 hours	Wearing the monitor is integral to the proposed intervention. Given the technical capabilities of the monitor, current wireless signals will only be available on the postpartum ward, therefore women will need to be present on the ward for the device to transmit signals to the central monitor and alerts to clinicians should abnormalities occur.
Exclusion Criteria	Rationale
1. Admitted to ICU directly after delivery	The ICU at MRRH is a closed unit in a separate building from the postpartum ward, as such, monitoring systems in use there are different from on the postpartum ward. The aim of this study is to investigate the use of wireless monitoring for women admitted to the postpartum ward after delivery.
2. Known allergies or hypersensitivity to device materials	For this research we will be limited to using standard electrode adhesives to apply the device. To avoid adverse reactions, any women with allergies or known hypersensitivity to the device will be excluded.

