Research assistants will be asked to document field notes at the time of consent to capture information on the length of time taken for the consent, if the participant had others present, and observations during the process of the consent (e.g. discussion by the participant with an attendant or family member)

If women are unconscious or in a mental state where they are unable to consent for themselves, an attendant or guardian will be approached for consent. As women in this condition are at high risk for morbidity and/or mortality inclusion in this study is key to achieve the objectives of reducing this risk. Additionally, women in this condition are the most likely to gain direct benefit from vital sign monitoring. As such if an attendant is not available the woman will be enrolled without consent to enable monitoring to begin immediately. Consent will be sought as soon as possible after the woman regains capacity to consent or an attendant becomes available. If the woman and/or her attendant declines to participate at that time all study procedures will be discontinued.

Study Procedures

1. A group meeting detailing the study background, procedures, risks and benefits will be held for all clinical providers in the department prior to study initiation.
2. We will obtain informed consent for clinicians and peripartum women admitted for delivery as described above.
3. A 2-hour training session on the use of the wireless monitoring system, nature of alerts and emergency mobile phone will be held for enrolled clinicians at a time convenient to them.
4. Alternative two-week blocks will be assigned to “intervention” vs “control”. During an “intervention block” all women delivering by emergency cesarean and consenting to participate will be monitored using the wireless device for the first 24 hours after delivery. During a “control

block" standard of care for monitoring will be used and women delivering via emergency cesarean will have record review only.

5. Maternity ward coverage schedules for enrolled specialist and midwives will be obtained. This will be used to determine the clinicians on call during each intervention block.
6. During the intervention block, midwives present in the theatre will be asked to perform the following tasks for any emergency cesarean deliveries s/he is present for:
 - a. Placement of the biosensor on any enrolled women s/he delivers by emergency cesarean delivery immediately after completion of the surgery.

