11. Every 24 hours a research assistant will perform medical chart review on enrolled participants to assess for documentation of the occurrence of any severe maternal outcome (Table 2). The research assistant will also review daily 24-hour reports generated by covering clinicians (standard maternity ward practice) to identify potential severe maternal outcomes not documented in the medical record.

Table 2: Severe Maternal Outcomes based on WHO Near Miss Criteria with demonstrated feasibility of collection in a RLS^{28,29,71}

Outcome	Definition/Measurement
Death	Mortality occurring at any time point after delivery and prior to discharge
Clinical based near-miss criteria	
Acute cyanosis	Blue or purple coloration of the skin or mucous membranes due to low oxygen saturation
Gasping	Terminal respiratory pattern, the breath is convulsively and audibly caught.
Severe bradypnea or tachypnea	Respiratory rate < 6 or Respiratory rate > 40
Shock	Persistent systolic BP ≤ 80 mmHg or a persistent systolic BP ≤ 90 mmHg with a HR ≥ 120.
Oliguria	Urinary output < 30 ml/hour for 4 hours or < 400 ml/24 hours non-responsive to fluids/diuretics.
Failure to form clots	Bedside clotting test or absence of clotting from the IV site after 7 minutes
Prolonged unconsciousness	Complete or near-complete lack of responsiveness to external stimuli.
Cardiac arrest	Sudden absence of pulse and loss of consciousness.
Stroke	Neurological deficit of cerebrovascular cause persisting ≥ 24 hours.
Uncontrollable fits	Refractory, persistent convulsions or status epilepticus.
Total paralysis	Complete or partial paralysis of both sides of the body.
Jaundice in the presence of pre-eclampsia	BP > 140/90) with proteinuria (> 1 + dipstick in ≥ 2 samples) and jaundice.
Laboratory-based near miss criteria	
Acute severe azotemia	Creatinine > 300 mmol/l or > 3,5 mg/dl
Severe acute hyperbilirubinemia	Bilirubin > 100 µmol/l or > 6.0 mg/dl.
Severe acute thrombocytopenia	<50 000 platelets/ml
Management-based near-miss criteria	
Use of continuous vasoactive drugs	Uninterrupted infusion of dopamine, epinephrine, or norepinephrine.
Hysterectomy	Surgical removal of the uterus following infection or hemorrhage.
Massive transfusion	Transfusion of ≥ 5 units of blood
Intubation and ventilation not related to anesthesia	Placement of an endotracheal tube or ventilation for > 60 minutes purposes other than anesthesia
Dialysis for acute renal failure	

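### The protocol gives two incompatible enrolment rules for incapacitated women with no attendant; they need reconciling, and the SAP should apply the resulting rule identically in both block types

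*Protocol*

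**What the plan says.** Three places in the protocol address a woman who cannot consent for herself.

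- Subject Selection, Peripartum Women, inclusion criterion 3 requires that she be "Able to provide consent or have a guardian/attendant present who can consent on their behalf".
- Subject Enrollment and Consent Procedures, Peripartum women, says an attendant or guardian is approached first, but "if an attendant is not available the woman will be enrolled without consent to enable monitoring to begin immediately". Consent is then sought as soon as she regains capacity or an attendant appears. On refusal, study procedures end.
- Risk/Discomforts and protections, in the item on having less than 24 hours between recruitment and consent, says "we have limited enrollment to those women who can either consent for themselves or who have a guardian available to consent".

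The two block types select women differently. Under Study Procedures, item 4, in intervention blocks "all women delivering by emergency cesarean and consenting to participate will be monitored using the wireless device", while in control blocks "women delivering via emergency cesarean will have record review only". For the control records the Study Intervention section says: "We request to waive consent for this record review only". Item 11 says that "a research assistant will perform medical chart review on enrolled participants".

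The SAP's Aim 1 analysis is by intention to treat. The intervention group includes eligible women who declined, were missed, were screened but not enrolled, or were enrolled but not monitored, and event rates in both periods are taken over all eligible women. The SAP section on monitoring use defines eligibility for monitoring as meeting the criteria in a block allocated to monitoring.

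**The concern.** The first problem is participant protection. The risk section tells the ethics boards that nobody is enrolled without her own or a guardian's consent, and the consent section sets out when that will happen. A board reading one section would approve something different from a board reading the other.

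The second problem is who is counted. The consent section itself describes these women as being at high risk, and prolonged unconsciousness is one of the SMO components. If they were left out of intervention blocks but kept in control blocks, the intervention rate would fall for a reason unrelated to monitoring. The question is whether the documents allow that, and how large it could be.

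**Working it through.** **Consistency.** Take a woman who is incapacitated, has no attendant and goes to the postpartum ward.

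- Consent section: enrolled, with deferred consent.
- Inclusion criterion 3: not eligible.
- Risk section: not enrolled.

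No reading satisfies all three. A woman with an attendant is enrolled under every one of them, and a woman admitted directly to the ICU is excluded by a separate criterion. The conflict concerns only the first type.

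**Where an imbalance could enter.**

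1. If the consent section governs, she is enrolled in intervention blocks and there is no imbalance at enrolment.
2. If criterion 3 governs and is applied to both block types, she is excluded from both and there is again no imbalance.
3. If criterion 3 governs but is applied only in intervention blocks, she is lost from one arm. This is possible because controls have record review only, and the extraction items listed in Study Procedures, item 12, include neither capacity nor presence of an attendant. (The chart review form in Appendix 1 is not among the documents.) A marginal comment in the SAP sees the same difficulty for women ineligible on language, who would not be identifiable among controls.
4. If she is enrolled and consent is later refused, the SAP would count her with the decliners. But study procedures stop, chart review is itself a listed procedure for enrolled participants, and the waiver covers control records only. Whether her outcome may be used is not stated.

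**Yardstick: the plan's own figure** (Protocol, Sample Size: 1,235 per group, 95 per block, ICC 0.01, baseline SMO rate 13%, two-sided 0.05, 80% power, difference 5.7 points).

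- Effective size: 1235 / (1 + 95 × 0.01) = 633.3, matching the stated 633. The usual form, 1235 / (1 + 94 × 0.01), gives 636.6.
- Power at 633 per group is 0.794 for a rise from 13% to 18.7% and 0.920 for a fall to 7.3%. The 5.7 points therefore reproduce for a rise; the reduction detectable with 80% power is 4.84 points.

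**Size under route 3.** Let f be the share of women affected and q their SMO rate. With a 13% control rate that includes them and no true effect, the intervention rate is (0.13 − f·q) / (1 − f). The documents give neither f nor q, so both are assumptions.

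| f | q = 30%: spurious benefit (points) | q = 100%: spurious benefit (points) |
|---|---|---|
| 0.5% | 0.09 | 0.44 |
| 1 in 112 (0.89%) | 0.15 | 0.78 |
| 1% | 0.17 | 0.88 |
| 2% | 0.35 | 1.78 |
| 3% | 0.53 | 2.69 |

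The 1-in-112 row uses the protocol's estimate of about 112 emergency cesareans per block, hence 112 × 0.13 = 14.56 expected events.

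- q = 100%: (14.56 − 1) / 111 = 12.22%.
- q = 30%: (14.56 − 0.3) / 111 = 12.85%.

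Across the table the bias is about 2% to 47% of the 5.7-point difference (0.09 / 5.7 to 2.69 / 5.7). At an effective 633 per arm, the chance of falsely declaring benefit, nominally 2.5%, becomes 2.8% to 32%. Under routes 1 and 2 the bias from this source is zero.

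**The case against.** A reader might infer that the highest-risk women are generally in the control group and missing from the intervention group. The documents do not support that. Incapacitated women with an attendant are enrolled under every section, direct ICU admissions are excluded, and intention to treat keeps eligible women in the intervention group even when consent was not obtained.

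A reader might also infer that the waiver means these women are always counted among controls. The waiver removes consent for record review; it does not remove the eligibility criteria, and the SAP restricts both periods to eligible women. Uneven application of criterion 3 is possible, but no section states it.

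It can fairly be added that the consent section is the specific operating instruction for these women, that it provides deferred consent with an exit, and that following it leaves no imbalance at enrolment. Nor do the documents say whether unconsciousness already present before delivery counts as an outcome event.

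All of this stands, and it limits the bias argument to a narrow route. It does not remove the contradiction. Intention to treat does not close the route either, because it depends on eligibility, eligibility depends on the criteria, and criterion 3 is one of the conflicting rules. The SAP's cohort section also still defines the intervention cohort as enrolled women, which does not match its Aim 1 analysis.

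**Conclusion.** The contradiction is definite: the consent section conflicts with inclusion criterion 3 and with the risk section's stated protection. It should be resolved whatever its numerical effect.

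The threat to the primary comparison is conditional. It requires either that criterion 3 be enforced in intervention blocks and not in control charts, or that outcomes be dropped after deferred consent is refused. Only incapacitated, unattended women not admitted directly to the ICU are affected, and the documents give no count of them. On the assumptions shown, the spurious benefit is about 0.1 to 2.7 points, and about 0.15 to 0.8 points at one woman per block. The upper figures assume that every such woman has an SMO, so they mark the edge of the range and are not an expected value.

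**What to change.** 1. Reconcile inclusion criterion 3, the consent section and the risk section with the ethics boards so that one rule stands. This review takes no position on which.
2. State in the SAP that the analysis population is defined by criteria ascertainable from records in both block types and applied identically. Women unable to consent are then either counted in both arms or excluded from both, according to the reconciled rule and whatever their later consent to monitoring. If the rule turns on capacity or presence of an attendant, both must be recorded in control blocks too.
3. Obtain ethics approval to use chart outcomes for women in intervention blocks who were not enrolled or who later declined, and state how those outcomes are collected.
4. Report, by block type, the number of women unable to consent and without an attendant.

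The cost is an ethics-board amendment that reconciles the enrolment text and extends the record-review waiver beyond controls, plus a short SAP edit. If capacity and attendant presence must be captured, the chart review form would also need to record them.
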